1.4 Study design

This is a Phase I, open-label, non-randomised, two-part study in patients with EGFRm+ NSCLC who have progressed on an EGFR TKI. Part A will assess the effect of rifampicin on the PK parameters of AZD9291 and metabolites AZ5104 and AZ7550 following multiple oral dosing of both rifampicin and AZD9291 in a fasted state.

Part B will allow patients further access to AZD9291 after the PK phase (Part A) and will provide for additional safety data collection.

This study will be conducted at approximately 16 sites across Asia, North America and Western Europe with approximately 38 patients enrolled and dosed to achieve at least 30 evaluable patients. Additional patients may be enrolled to ensure the minimum number of evaluable patients. For a patient to be evaluable the patient must have completed the required PK collections for the primary comparison (AZD9291 and rifampicin combined [Period 2] compared to AZD9291 administered alone [Period 1]).

Part A

[figure not shown]
Part A is a non-randomised, open-label, 3-period design. A study flow chart for Part A is presented in [Figure 1](#). Patients will receive AZD9291 80 mg once daily for 77 days (Days 1 to 77). Patients will also receive oral daily doses of rifampicin for 21 days (Days 29 to 49) concurrently with AZD9291.

Part B

On completion of Part A, patients may continue to take AZD9291 tablets (80 mg once daily) in Part B if they and the Investigator agree that this is appropriate. Patients should start Part B immediately (ie, 24 hours) after the last dose received in Part A (Day 78 after the 24-hour sample collection). Patients will have weekly clinic visits for the first 4 weeks; thereafter visits will be every 4 weeks. Safety assessments will be collected and there will be no formal evaluation of efficacy. Patients' medical/oncological care will be according to local clinical practice. Part B will be of approximately 12 months' duration from the date the last patient enters this part of the study (allowing for any scheduled Part B follow-up assessments).

During and after Part B, patients may continue to take AZD9291, if they and the Investigator deem it appropriate, until such time as the Investigator believes they are no longer deriving clinical benefit or they stop taking AZD9291 for any other reason. After the end of Part B (approximately 12 months after the last patient entered Part B), patients will be seen as per their normal routine clinical schedule. No clinical data will be collected for those patients who continue to receive AZD9291 as part of continued access, other than the data specified in [Section 7.8](#).

Figure 1 Study flow chart – Part A

^a For patients who withdraw from the study prematurely and who do not participate in Part B

2. STUDY OBJECTIVES

2.1 Primary objective

Part A: To investigate the effect of multiple oral dosing of rifampicin on the steady-state exposure of AZD9291 ($C_{ss,max}$ and AUC_{τ}), following oral dosing in patients with EGFRm+ NSCLC following progression on a EGFR TKI.

2.2 Secondary objective

Part A: To characterise the PK of AZD9291 and metabolites (AZ5104 and AZ7550) following oral dosing of the tablet formulation in the presence and absence of rifampicin.

2.3 Safety objectives

Part A: To examine the safety and tolerability of AZD9291 in patients with EGFRm+ NSCLC in the presence and absence of co-administered rifampicin.

Part B: To examine the safety and tolerability of AZD9291 following extended administration in patients with EGFRm+ NSCLC.

2.4 Exploratory objectives

Part A: To assess the induction potential of AZD9291 on CYP3A4.

Part A: To perform genetic research in the AZD9291 clinical pharmacology development programme to explore how genetic variations may affect the clinical PK of AZD9291.

Part A: To provide data to allow analysis using population PK approaches.

2.5 Outcome variables

Analysis: Part A	Outcome Measures:
PK	
Primary AZD9291	
 $C_{ss,max}$ and AUC_{τ} (alone [Day 28] and in combination with rifampicin [Day 49])
Secondary AZD9291	
 AUC_{τ}, and $C_{ss,max}$ [Day 77]; $t_{ss,max}$, $C_{ss,min}$, and CL_{ss}/F in all periods trough concentrations on Days 7, 14, 21, and 28 of Period 1, and Days 35, 42, and 49 of Period 2, and Days 56, 63, 70, and 77 of Period 3
Secondary AZ5104 and AZ7550	
 AUC_{τ}, $C_{ss,max}$, $t_{ss,max}$, $C_{ss,min}$, and metabolic ratios (AZ5104 to AZD9291 and AZ7550 to AZD9291), $MRAUC_{\tau}$ and $MRC_{ss,max}$ in all periods trough concentrations on Days 7, 14, 21, and 28 of Period 1, and Days 35, 42, and 49 of Period 2, and Days 56, 63, 70, and 77 of Period 3

Secondary rifampicin	
 • AUC_{τ}, $C_{ss,max}$, $t_{ss,max}$, $C_{ss,min}$, and CL_{ss}/F
Exploratory 4 β -hydroxy-cholesterol	
 • 4β-hydroxy-cholesterol at baseline and collected throughout the 77-day AZD9291 dosing period

Safety analysis : Part A and B	Outcome Measures :
	
 • AEs/SAEs graded by CTCAE (version 4) • Vital signs (blood pressure/pulse/temperature/height/weight) • Laboratory parameters (clinical chemistry/haematology/urinalysis) • Physical examination • Standard 12-lead ECGs • Echocardiogram/multiple gated acquisition scan (MUGA)

3. PATIENT SELECTION, ENROLMENT, RESTRICTIONS, DISCONTINUATION AND WITHDRAWAL

Each patient should meet all of the inclusion criteria and none of the exclusion criteria for this study. Under no circumstances can there be exceptions to this rule.

3.1 Inclusion criteria

For inclusion in the study patient should fulfil the following criteria:

1. Provision of written informed consent prior to any study-specific procedures. Procedures performed for routine clinical practice before the provision of written consent are acceptable if not intentionally done for study purposes.
2. Male or female, aged at least 18 years.
3. Histological or cytological confirmation diagnosis of NSCLC.
4. Radiological documentation of disease progression while on a previous continuous treatment with an EGFR TKI, eg gefitinib, erlotinib or afatinib. In addition, other lines of therapy may have been given. All patients must have documented radiological progression on the last treatment administered prior to enrolling in the study.
5. Confirmation that the tumour harbours an *EGFR* mutation known to be associated with EGFR TKI sensitivity (including G719X, exon 19 deletion, L858R, L861Q).

6. Eastern Cooperative Oncology Group (ECOG) performance status 0-1 with no deterioration over the previous 2 weeks ([Appendix G](#)).
7. Patients must have a life expectancy of ≥ 12 weeks as estimated at the time of screening.
8. Females should be using adequate contraceptive measures and must have a negative pregnancy test prior to start of dosing if of child-bearing potential, or must have evidence of non-child-bearing potential by fulfilling one of the following criteria at screening:
 - Post-menopausal defined as aged more than 50 years and amenorrhoeic for at least 12 months following cessation of all exogenous hormonal treatments
 - Women under 50 years old would be considered post-menopausal if they have been amenorrhoeic for 12 months or more following cessation of exogenous hormonal treatments and with LH and FSH levels in the post-menopausal range for the institution
 - Documentation of irreversible surgical sterilisation by hysterectomy, bilateral oophorectomy, or bilateral salpingectomy, but not tubal ligation.
9. Patients are willing and able to comply with the protocol for the duration of the study including undergoing treatment and scheduled visits and examinations.
10. Male patients should be willing to use barrier contraception, ie, condoms, until 6 months after last study drug is taken.
11. For inclusion in **optional genetic research**, patients must provide separate informed consent. If a patient declines to consent to optional genetic research, this does not exclude the patient from participating in any aspect of the study.
12. Contact lens wearers must be prepared to not wear contact lenses and wear glasses for the duration of the rifampicin dosing.

3.2 Exclusion criteria

Patients should not enter the study if any of the following exclusion criteria are fulfilled:

1. Involvement in the planning and/or conduct of the study (applies to both AstraZeneca staff and/or staff at the study site).
2. Previous enrolment and dosing in the present study. Patients who were enrolled, screened but not dosed (ie, withdrew from the study prior to dosing) may be re-enrolled and re-screened if in the opinion of the Investigator, the reason(s) for earlier withdrawal no longer applies.

3. Participation in another clinical study with an IP during the last 14 days (or a longer period depending on the defined characteristics of the agents used).
4. Treatment with any of the following:
 - Treatment with an EGFR TKI (eg, erlotinib or gefitinib) within 8 days or approximately 5 x half-life, whichever is the longer, of the first dose of study treatment
 - Any cytotoxic chemotherapy, investigational agents or other anticancer drugs from a previous treatment regimen or clinical study within 14 days of the first dose of study treatment
 - Major surgery (excluding placement of vascular access) within 4 weeks of the first dose of study treatment
 - Radiotherapy with a limited field of radiation for palliation within 1 week of the first dose of study treatment, with the exception of patients receiving radiation to more than 30% of the bone marrow or with a wide field of radiation which must be completed within 4 weeks of the first dose of study treatment
 - Patients currently receiving (or unable to stop use prior to receiving the first dose of study treatment) medications or herbal supplements known to be potent inhibitors of CYP3A4 (at least 1 week prior) and potent inducers of CYP3A4 (at least 3 week prior). All patients in Part B and continued access must avoid concomitant use of any medications, herbal supplements and/or ingestion of foods with known potent inducer effects on CYP3A4 ([Appendix H](#)).
5. Any unresolved toxicities from prior therapy greater than CTCAE Grade 1 at the time of starting study treatment with the exception of alopecia and Grade 2, prior platinum-therapy related neuropathy.
6. Any intake of grapefruit, grapefruit juice, Seville oranges, Seville orange marmalade, or other products containing grapefruit or Seville oranges within 7 days of the first administration of the IP until the final PK sample collection on Day 78 of Part A.
7. Spinal cord compression or brain metastases unless asymptomatic, stable and not requiring steroids for at least 4 weeks prior to start of study treatment.
8. Any evidence of severe or uncontrolled systemic diseases, including uncontrolled hypertension and active bleeding diatheses, which in the Investigator's opinion makes it undesirable for the patient to participate in the study or which would jeopardise compliance with the protocol, or active infection including hepatitis B,

hepatitis C and human immunodeficiency virus (HIV). Screening for chronic conditions is not required.

9. Inadequate bone marrow reserve or organ function as demonstrated by any of the following laboratory values:
 - Absolute neutrophil count $<1.5 \times 10^9/L$
 - Platelet count $<100 \times 10^9/L$
 - Haemoglobin $<90 \text{ g/L}$
 - Alanine aminotransferase (ALT) >2.5 times the upper limit of normal (ULN) if no demonstrable liver metastases or >5 times ULN in the presence of liver metastases
 - Aspartate aminotransferase (AST) >2.5 times ULN if no demonstrable liver metastases or >5 times ULN in the presence of liver metastases
 - Total bilirubin >1.5 times ULN if no liver metastases or >3 times ULN in the presence of documented Gilbert's Syndrome (unconjugated hyperbilirubinaemia) or liver metastases
 - Creatinine >1.5 times ULN concurrent with creatinine clearance $<50 \text{ ml/min}$ (measured or calculated by Cockcroft and Gault equation); confirmation of creatinine clearance is only required when creatinine is >1.5 times ULN.
10. Any of the following cardiac criteria:
 - Mean resting corrected QT interval corrected for heart rate using Fridericia's correction factor (QTcF) $>470 \text{ msec}$ obtained from 3 electrocardiograms (ECGs)
 - Any clinically important abnormalities in rhythm, conduction or morphology of resting ECG eg, complete left bundle branch block, third degree heart block, second degree heart block, PR interval $>250 \text{ msec}$
 - Any factors that increase the risk of QTc prolongation or risk of arrhythmic events such as heart failure, hypokalaemia, congenital long QT syndrome, family history of long QT syndrome or unexplained sudden death under 40 years of age or any concomitant medication known to prolong the QT interval ([Appendix H](#)).
11. Patients unable to swallow orally administered medication or patients with gastrointestinal disorders or significant gastrointestinal resection likely to interfere with the absorption of AZD9291.

12. Past medical history of ILD, drug-induced ILD, radiation pneumonitis which required steroid treatment, or any evidence of clinically active ILD.
13. Women who are breastfeeding.
14. Patients with a known hypersensitivity to AZD9291 or any of the excipients of the product.
15. Judgement by the Investigator that the patient should not participate in the study if the patient is unlikely to comply with study procedures, restrictions and requirements.
16. Patients with a known hypersensitivity to rifampicin or any of the excipients of the product.
17. Concomitant medication contraindicated for use with rifampicin (including, but not limited to): cisapride, oral midazolam, nisoldipine, pimozide, quinidine, dofetilide, triazolam, levacetylmethadol (levomethadyl), 3-hydroxy-3-methyl-glutaryl coenzyme A (HMG-CoA)-reductase inhibitors metabolised by CYP3A4, such as lovastatin and simvastatin, ergot alkaloids metabolised by CYP3A4, such as dihydroergotamine, ergometrine (ergonovine), ergotamine and methylergometrine (methylergonovine).

In addition, the following is considered a criterion for exclusion from the exploratory genetic research:

18. Previous allogenic bone marrow transplant.
19. Non-leukocyte depleted whole blood transfusion within 120 days of the date of the genetic sample collection.

Procedures for withdrawal of incorrectly enrolled patients see Section 3.4.

3.3 Patient enrolment

The Principal Investigator(s) or designee will:

1. Obtain signed informed consent from the potential patient before any study-specific procedures are performed.
2. Assign each potential patient a unique enrolment code (E-code) beginning with 'E#' after written informed consent has been obtained. The E-code (EWWXXYZZ) will consist of a 2-digit country number (WW), a 2-digit site number (XX), a 1-digit study number (Y) and a 2-digit patient number (ZZ, starting with 01) issued by the study centre in order of informed consent taken.
3. Determine patient eligibility. See Section 3.1 and 3.2.

If a patient withdraws from participation in the study, then his/her enrolment numbers cannot be reused.

Patients who were enrolled, screened but not dosed (ie, withdrew from the study prior to dosing) may be re-enrolled and re-screened if, in the opinion of the Investigator, the reason(s) for earlier withdrawal no longer applies. Such patients will be given a new enrolment code upon re-enrolment. Patients cannot re-enter the study if dosed and subsequently withdrawn from the study. Patients who discontinue their participation in Part A prematurely may still be eligible to continue to take AZD9291 in Part B, if the Investigator believes it is in the patient's interest, ie, discontinuation from Part A may not necessarily result in withdrawal from the study.

3.4 Procedures for handling incorrectly enrolled patients

Patients who fail to meet the eligibility criteria should not, under any circumstances, be enrolled or receive study medication. There can be no exceptions to this rule.

Where patients who do not meet the selection criteria are enrolled in error or incorrectly started on study treatment, or where patients subsequently fail to meet the study criteria post-initiation, a discussion should occur between the AstraZeneca Physician or his/her representative and the Investigator regarding whether to continue or discontinue the patient from study treatment. Once a decision is made, Investigators need to ensure they comply with all applicable requirements for human patient protection and ethical review.

The AstraZeneca Physician or representative is to ensure all such decisions are appropriately documented. In situations where an agreement cannot be reached, the patient should have their study treatment stopped and be withdrawn from the study.

3.5 Methods for assigning treatment groups (not applicable)

3.6 Methods for ensuring blinding (not applicable)

3.7 Methods for unblinding (not applicable)

3.8 Restrictions

The following restrictions apply while the patient is receiving study treatment and for the specified times before and after:

1. Females of child bearing potential should use reliable methods of contraception ([Appendix F](#)) from the time of screening until 6 months after discontinuing study treatment. Acceptable methods of contraception include total sexual abstinence, tubal ligation, hormonal contraceptives that are not prone to drug-drug interactions (IUS Levonorgestrel Intra Uterine System [Mirena], Medroxyprogesterone injections [Depo-Provera]), copper-banded intra-uterine devices and vasectomised partner. All hormonal methods of contraception should be used in combination with the use of a condom by their male sexual partner for intercourse.

2. Male patients should be asked to use barrier contraceptives (ie, by use of condoms) during sex with all partners during the study and for a washout period of 6 months. Where a sexual partner of a male participant is a woman of child-bearing potential, patients should avoid procreation for 6 months after completion of study treatment. Patients should refrain from donating sperm from the start of dosing until 6 months after discontinuing study treatment. If male patients wish to father children they should be advised to arrange for freezing of sperm samples prior to the start of study treatment.
3. In Part A, patients should not consume any grapefruit, grapefruit juice, Seville oranges, Seville orange marmalade, or other products containing grapefruit or Seville oranges within 7 days of the first administration of the IP until the final PK sample collection on Day 78.
4. Patients who wear contact lenses must discontinue wearing their lenses if they have any mild to moderate eye symptoms (CTCAE Grade ≤ 2) while receiving treatment with AZD9291 until at least 1 week after symptoms have resolved. If a patient has a recurrence of eye symptoms or experiences any severe (CTCAE Grade ≥ 3) ocular events, they must discontinue wearing their contact lenses until at least 1 week after treatment with AZD9291 is permanently discontinued. Patients must not use any eye drops or ointment for treatment of eye symptoms, unless agreed by a study doctor, at any time during the study until 1 week after AZD9291 has been permanently discontinued. Patient should consult the clinic/hospital promptly if they have any concerns.
5. Patients should maintain a consistent diet during Part A of the study and should not change their diet between study periods (Periods 1, 2 and 3 of Part A).

Details of restrictions related to concomitant medications can be found in Section [7.7](#).

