Appendix F
Acceptable Birth Control Methods

ACCEPTABLE BIRTH CONTROL METHODS

AZD9291 is regarded as a compound with medium/high foetal risk.

Patients of childbearing potential and their partners, who are sexually active, must agree to the use of 2 highly effective forms of contraception throughout their participation in the study and for 6 months after last dose of study drug.

Acceptable non-hormonal birth control methods include:

- Total sexual abstinence. Abstinence must be for the total duration of the trial and until 6 months after discontinuation of study treatment.
- Vasectomised sexual partner plus male condom. With participant assurance that partner received post-vasectomy confirmation of azoospermia.
- Tubal occlusion plus male condom with spermicide
- IUD plus male condom + spermicide. Provided coils are copper-banded

Acceptable hormonal methods that are not prone to drug-drug interactions:

- IUS Levonorgestrel Intra Uterine System (Mirena) + male condom with spermicide
- Medroxyprogesterone injections (Depo-provera) + male condom with spermicide.

Clinical Study Protocol Appendix G

Drug Substance	AZD9291
Study Code	D5160C00013
Edition Number	1
Date	

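### Section 3.8 item 1 gives a looser contraception list than the Appendix F it cites: three methods lose the condom and four lose the spermicide

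*Protocol*

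**What the plan says.** Section 3.8 item 1 opens with "Females of child bearing potential should use reliable methods of contraception" and cites Appendix F, with the requirement running from screening until 6 months after study treatment stops. It then sets out what is acceptable: "Acceptable methods of contraception include total sexual abstinence, tubal ligation, hormonal contraceptives that are not prone to drug-drug interactions" (the levonorgestrel intra-uterine system and medroxyprogesterone injections are named), followed by "copper-banded intra-uterine devices and vasectomised partner". The item ends with its only condom rule: "All hormonal methods of contraception should be used in combination with the use of a condom by their male sexual partner for intercourse". It does not mention spermicide or confirmation that a vasectomy worked.

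Appendix F classes AZD9291 as a compound with medium to high foetal risk. It says that sexually active patients of childbearing potential and their partners "must agree to the use of 2 highly effective forms of contraception", during the study and for 6 months after the last dose. Besides total abstinence, its non-hormonal options are "Vasectomised sexual partner plus male condom. With participant assurance that partner received post-vasectomy confirmation of azoospermia", "Tubal occlusion plus male condom with spermicide" and "IUD plus male condom + spermicide. Provided coils are copper-banded". Its two hormonal options, the levonorgestrel system and medroxyprogesterone, are each combined with a male condom and spermicide.

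Inclusion criterion 8 (Section 3.1) asks only for adequate contraceptive measures and does not define them. It does not accept tubal ligation as evidence of non-child-bearing potential.

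**The concern.** Section 3.8 does more than refer the reader to the appendix. It states which methods are acceptable and asks for a condom only when describing hormonal methods. A reader would naturally conclude that the non-hormonal methods need none. Under Appendix F a condom rule confined to hormonal methods would make no sense, because the non-hormonal methods other than abstinence need one too.

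What is at stake is patient safety and consistent conduct. The study runs at about 16 sites across three regions, and two sites could apply different rules while each cites the protocol. A woman using a copper device alone complies with the Section 3.8 list and breaches Appendix F. The rule has to hold through 77 days of Part A, through Part B (which ends about 12 months after the last patient enters it), through any continued access, and for 6 months afterwards. The pregnancy tests in the study plan detect a pregnancy but do not prevent one. In Part B the footnote to the study plan provides for a test on suspicion and at the 30-day follow-up, so more rests there on correct contraception instructions.

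**Working it through.** The plan gives no figure to reproduce here; the check is a comparison of the two lists, entry by entry. Tubal ligation (Section 3.8) and tubal occlusion (Appendix F) are read as the same method.

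| Appendix F entry | Second element in Appendix F | What Section 3.8 item 1 asks | Missing from Section 3.8 |
|---|---|---|---|
| Total abstinence | none | none | nothing |
| Vasectomised partner | condom; azoospermia assurance | nothing further | condom, azoospermia assurance |
| Tubal occlusion | condom, spermicide | nothing further | condom, spermicide |
| Copper-banded device | condom, spermicide | nothing further | condom, spermicide |
| Levonorgestrel system | condom, spermicide | condom | spermicide |
| Medroxyprogesterone | condom, spermicide | condom | spermicide |

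Counts from the table:

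- Condom missing: vasectomised partner, tubal occlusion, copper device = 3.
- Spermicide missing: tubal occlusion, copper device, levonorgestrel system, medroxyprogesterone = 4.
- Azoospermia assurance missing: vasectomised partner = 1.
- Overlap: tubal occlusion and the copper device lack both condom and spermicide (2); the vasectomised partner lacks both condom and azoospermia assurance (1).
- Entries differing in any respect: 3 + 4 + 1 − 2 − 1 = 5 of 6. Only abstinence agrees.

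Every difference runs the same way: Section 3.8 never asks for more than Appendix F. A site that follows Appendix F therefore satisfies both texts, and a site that follows the Section 3.8 list does not. The 6-month period after treatment is the same in both places.

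Criterion 8 does not settle the matter. A woman whose only relevant history is a tubal ligation still counts as being of child-bearing potential, so the contraception rule applies to her. Section 3.8 then lists that same ligation, by itself, as acceptable contraception.

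**The case against.** The best defence is that Section 3.8 defers to Appendix F. The citation stands in the operative sentence, the list that follows is introduced as what acceptable methods include, and every method named is also in the appendix. On that view the list is an incomplete summary, and the appendix, which has the mandatory wording, governs. The closing sentence does not say that only hormonal methods need a condom. Spermicide and azoospermia are details that a body section may reasonably leave to an appendix, so the substantive gap is three methods, not five. The protocol also states no order of precedence, and Appendix F is marked Edition 1 while the protocol body is Edition 2, so the sponsor's intention is not certain.

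Part of this stands. The condom gap for three methods is the substance; the spermicide and azoospermia differences are lesser omissions. The exemption for non-hormonal methods is implied, not stated. The harm depends on a site working from the body text without opening the appendix.

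It does not remove the conflict. A summary may drop detail, but this one turns a two-method requirement into what reads as permission for one method. If tubal ligation and tubal occlusion were different methods, Appendix F would not list ligation at all and the conflict would be wider. The edition numbers do not matter for the remedy, because the stricter text satisfies both.

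**Conclusion.** The concern holds. Section 3.8 item 1 is inconsistent with the appendix it cites and is wrong as written. Five of the six Appendix F entries differ. The part that matters is the three methods (tubal ligation, copper device, vasectomised partner) that Section 3.8 lists without the condom Appendix F requires.

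Severity is low. The single-method gap touches only women of child-bearing potential who rely on one of those three methods, in a study of about 38 patients. The documents do not give their number. The primary pharmacokinetic comparison, the sample size and the analysis sets are untouched. This is an internal inconsistency in a safety instruction, and it should be corrected because the drug carries a stated foetal risk and the correction is simple. The count assumes that tubal ligation and tubal occlusion mean the same method.

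**What to change.** Let Appendix F prevail. In Section 3.8 item 1, delete the list of methods and the sentence on condoms with hormonal methods. Replace them with a statement that women of child-bearing potential must use one of the combinations in Appendix F (2 forms, or total sexual abstinence) from screening until 6 months after the last dose of study treatment. Appendix F needs no change.

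The cost is a wording change to one item in one amendment, with no added visit, procedure or data item.
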